Frequently sampled intravenous glucose tolerance test (FSIGT): All studies will be conducted in the follicular phase in controls and during amenorrhea in PCOS women. Each subject will be instructed to drink only water during the 12-hour fasting period before the FSIGT, and to avoid caffeinated fluid intake. Glucose in the form of a 50% solution (0.3 g/kg) and regular human insulin (0.03 units/kg) will be injected through an intravenous line at 0 and 20 min, respectively. Blood will be collected at -20, -15, -5, 0, 2, 4, 8, 19, 22, 30, 40, 50, 70, 90, and 180 min for glucose and insulin determinations. Approximately 2-3 tablespoons (28-42 ml) will be drawn for the FSIGT test. Adipocytes isolation and culture: Approximately 1.0 gm of fat will be obtained from the lower SC abdomen using standard procedures under local anesthesia. Adipocytes and the stromal vascular fraction will be isolated to measure adipocyte cell number and diameter, lipid accumulation and function, adiponectin, and stem cell development.

Procedures: All procedures will be performed in normal and PCOS women at the start of study.

i). Venipuncture: Fasting blood will be collected for blood count, chemistry panel, LH, FSH, total/free T, DHT, A4, DHEAS, E1, E2, anti-mullerian hormone (AMH), SHBG, adiponectin, IL-6,lipid profile, C-reactive protein, glucagon, leptin, C-peptide, and FFAs. Blood samples for all participants will be shipped to Oregon State Health University (OHSU) for analysis of AMH, IL-6, adiponectin, glucagon, leptin, and C-peptide levels. The University of Michigan will perform a comprehensive hormone analysis by LC-MS/MS, including traditional (T, AD, DHEA, DHEAS) and emerging androgen biomarkers (11-oxygenated C19 steroids, 11 OHA, 11KA, 11OHT, 11KT). There will be no personal identifiers on the samples that sent to OHSU or University of Michigan.

Study numbers will be used.

ii). Body composition: Body composition will be assessed by BMI, waist-to-hip circumference and DXA scanning. Girths will be measured at the waist (narrowest section of the torso between ribs and umbilicus) and hips (largest protrusion of the hip region, above the gluteal fold). For total body fat and regional fat distribution (central vs. appendicular), whole body scans will be performed, utilizing DXA imaging (Hologics QDR 1500). A portable BIA will calculate lean body mass changes by computerized methods to measure resistance and reactance.

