• Subjects will be asked to ingest only a clear liquid diet beginning at midnight on the day of the MRI and DXA scan.

• Their bone density and body fat composition will be assessed by a test called a DXA Scan.

• It is estimated that this visit will take approximately 2 hours.

• The medical images will be performed at UCLA. The imaging studies are performed as part of this research study and will not be reviewed or interpreted by a UCLA radiologist. Any information regarding the imaging findings should be directed to the study PI

Revised 3-7-18 UCLA IRB #12-001780 Page 14 of 27

Removal of Abdominal Fat

- In order to be sure that participants are not ovulating, approximately ½ teaspoon (2 ml's) of blood may be drawn and sent to the laboratory for an immediate test of your progesterone level before the removal of fat. If the progesterone test indicates that you are ovulating, the fat removal may not be able to be performed that day and may need to be rescheduled.
- Subjects will be asked to ingest only a clear liquid diet beginning at midnight on the day of the procedure to remove abdominal fat.

• Subjects will be given local anesthetic and a small amount of fat approximately the size of a quarter will be removed from under the skin in their lower abdomen.

- Subjects will be asked to ingest only a clear liquid diet beginning at midnight on the day of the procedure to remove abdominal fat.
- It is estimated that this visit will take approximately 2 hours.

Follicle Stimulating Hormone (FSH) Stimulation Test and Ultrasound of the Ovaries

• Subjects will undergo a transvaginal ultrasound.

o Subjects will undergo a Follicle Stimulating Hormone (FSH) stimulation test. FSH is the hormone that normally induces the ovary to develop a follicle and a single injection of FSH predicts how sensitive the ovary is to FSH. Their blood will be drawn at -90, -60, -30 minutes and time 0 as well as at 1/2, 1, 1 1/2, 2, 3, 4, 6, 8, 10, 12, 16, 20, and 24 hours after the injection. In order to prevent multiple needle sticks for the blood draws, a catheter will be placed in a vein in their arm before the first blood draw. Their blood will be drawn at the intervals described above through the catheter.

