• Complete a diary regarding what time they took the pill, whether they had any menstrual bleeding, any changes in their health, any medications they took, if they exercised that day, and a brief summary of their diet.

• Collect a sample of their first morning urine once a week and store it until their next clinic visit. Subjects will be given instructions on the collection and storage of the samples.

• Return to the UCLA Clinic once a month for the following:

o A brief physical exam including a measurement of their height, weight, waist, and hips. Review any symptoms subjects may have experienced during the past month.

o Bring their prescription bottles so that the pills can be counted.

o Bring their weekly urine samples.

o Bring their completed diaries.

o Have blood tests (serum pregnancy test, complete blood count, and comprehensive metabolic panel) – approximately 1 teaspoon (5 ml) of blood will be drawn.

o After the third and sixth cycle, subjects will be asked to complete questionnaires regarding their feelings about various areas of their health and the quality of their life. Subjects have the right to refuse to answer any questions that they do not wish to answer. • After the third and sixth cycle, subjects will also have an assessment of their skin, and a transvaginal ultrasound of their ovaries.

• It is estimated that each of these visits will take approximately 1 hour

• Subjects will receive be reimbursed for their parking expenses and receive \$240after all 6 visits have been completed.

• Subjects will be asked to continue taking the flutamide or placebo until the procedures listed below are completed. Every effort will be made to complete all study visits as soon as possible.

After Completing Flutamide/Placebo

The FSIGT, MRI, DXA, Removal of Abdominal Fat, and FSH tests will be repeated as described above. Please note that a testosterone blood test, complete blood count, and comprehensive metabolic panel will be performed at the post-treatment FSH test.

30 Days after Last Pill

o Physical Exam

o Blood tests (pregnancy test, complete blood count, and comprehensive metabolic panel) - approximately 1 teaspoon (6 ml) of blood will be drawn from their vein.

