Potential problems during the collection of the subcutaneous abdominal fat specimens include a temporary discomfort from the local injection of anesthetic and/or pain, bleeding, and infection at the site of the lower abdominal incision. In very rare circumstances, local injection of anesthetic and/or the removal of abdominal fat may be associated with fainting with or without convulsions. Only experienced surgeons will perform the procedure to remove the small amount of fat, which should not significantly distort the contour of the abdominal skin.

Risks of Frequently-Sampled Intravenous Glucose Tolerance Test:

Insulin (introduced into your body during the intravenous glucose tolerance test) is the 1body's natural hormone for lowering blood sugars. If your blood sugars fall rapidly, you may experience mild dizziness, nausea, vomiting, shortness of breath, increased heart rate or sweating. If these effects occur, they are easily detected and treated with administration of supplemental sugar through the indwelling catheter, thereby raising the blood sugar. This condition is only temporary and has no known long-term health impact. The glucose (commonly called sugar) infused through the catheter as part of the intravenous glucose tolerance test may cause an initial feeling of warmth and flushing of the face, which are both transient symptoms that rapidly resolve. You will be asked to arrive for your testing after having fasted from midnight the night before. In light of the prolonged fast, you may feel hungry during the testing.

Risks of Follicle Stimulating Hormone (FSH) Stimulation Test.

Participants may experience lower abdominal bloating and/or vaginal spotting from this test.

Risks of DXA Scan:

Since the radiation procedures are all standard of care, the amount of radiation Subjects will receive is the same as that for similar patients who are not participating in this study. Therefore, they will not be exposed to any additional radiation by participating in this study.

Risks of Magnetic Resonance Imaging (MRI):

The MRI procedure uses a powerful magnetic field to generate detailed images of the body. The magnet could move objects within their body that contain metal, such as implants, clips and pacemakers. Subjects will be asked to tell the doctor if they have any metal items within their body.

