MRI scanning is painless but they might experience discomfort in the machine. In particular, loud beeping and hammering noises occur during the study when the

scanner is collecting measurements. Subjects also may be bothered by feelings of claustrophobia when placed inside the MRI, or by lying in one position for a long time. Subjects might also experience stimulation of the nerves in their body, which feels like a gentle tap or sensation of mild electric shock.

Because the risks to a fetus from MRI are unknown, subjects cannot participate in this study if they are pregnant.

Known Reproductive Risks:

Subjects should not become pregnant while on this study because the drugs in this study and the DXA scan can affect an unborn baby. Women should not breastfeed a baby while on this study. Therefore, subjects will need to use effective birth control while on this study. Examples of acceptable types of birth control are a diaphragm with spermicidal jelly, condoms, or an IUD (without hormones). Subjects should use birth control starting at the beginning of their participation in this study.

Unknown Risks to Women of Child Bearing Potential and Pregnant Women:

Flutamide can occasionally induce ovulation in a woman with PCOS who does not ovulate. This is important because this medication blocks androgen action and can impair the ability of androgen to normally induce development of the external genitalia in the male fetus. For this reason, if subjects believe that they are pregnant or have a chance of becoming pregnant they should not participate in this study. A serum pregnancy test will be performed before the start of study procedures and monthly throughout their participation in this study. If they are pregnant, the will not be allowed to participate in the study. If women do participate in this study, they must use a medically effective form of birth control before entering the study, while participating in the study, and for at least one month after stopping the study. If they become pregnant during the study, they will be asked to tell the researchers right away.

Unknown Risks to Infants:

The side effects of Flutamide on infants are not known, therefore if women are currently breastfeeding they cannot participate in this study.

Loss of Confidentiality:

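### The DXA risk text says taking part adds no radiation; this is false for healthy controls and unsupported for women with PCOS

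*Combined protocol and SAP*

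**What the plan says.** The Potential Risks section opens its list as a restatement of the consent form. Under Risks of DXA Scan it gives a premise, "Since the radiation procedures are all standard of care", equates subjects' exposure with that of comparable patients outside the study, and concludes: "Therefore, they will not be exposed to any additional radiation by participating in this study".

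Other parts of the protocol describe the scans differently:

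- Research Design and Methods, Aim 1, lists whole-body DXA as a measure of body composition and fat distribution, and says of the baseline work-up: "All procedures will be performed in normal and PCOS women at the start of study".
- Inclusion Criteria describes the controls as healthy, with no sign of endocrine dysfunction.
- Procedures places the MRI and DXA visit under the heading for women with and without PCOS, and says: "The imaging studies are performed as part of this research study and will not be reviewed or interpreted by a UCLA radiologist".
- Procedures, After Completing Flutamide/Placebo, says for women with PCOS: "The FSIGT, MRI, DXA, Removal of Abdominal Fat, and FSH tests will be repeated as described above".
- Known Reproductive Risks says that "the drugs in this study and the DXA scan can affect an unborn baby".

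**The concern.** The risk text makes a factual claim, that taking part adds no radiation, and applies it to every subject. It does not say the added exposure is small. If the scans happen only because of the trial, the claim is wrong whatever the dose.

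Accurate disclosure to participants is at stake. They are women aged 18 to 35, and some are healthy volunteers for whom the Potential Benefits section describes no direct benefit. Nothing statistical depends on the answer.

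**Working it through.** There is no plan figure to reproduce beyond the implied zero added exposure. The check sets the sections side by side and then counts scans.

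**1. Which procedures does the sentence cover?** The risk section calls ultrasound non-ionizing and describes MRI as using a magnetic field. DXA is the only ionizing study procedure described, so the statement about radiation procedures can only mean the DXA scans.

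**2. Controls.** The baseline procedures apply to them, the DXA visit is listed for them, and they are healthy by definition. Procedures says the scan measures bone density and body fat, but no section gives a clinical reason for measuring either in a control. The imaging is stated to be part of the research. There is therefore no usual care in the protocol that would include this scan, and the statement fails.

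**3. Women with PCOS.** The research-imaging sentence covers their scans too, and no clinical indication is given. The second scan belongs to the assessments after six 28-day cycles of flutamide or placebo, a time point that the trial creates. The protocol does not describe usual PCOS care, so this is strong inference and falls short of proof. The standard-of-care claim has nothing in the document to support it.

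**4. Scans per woman.** Controls finish after the baseline tests, so they have 1. PCOS completers have baseline plus post-treatment, so they have 2.

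**5. Count.** Scans = controls × 1 + PCOS women × 2.

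| Basis | Controls | PCOS | Scans |
|---|---|---|---|
| Planned completers (Aim 1; Inclusion Criteria) | 12 | 36 | 12 × 1 + 36 × 2 = 84 |
| Lay Summary enrolment, no dropout | 20 | 50 | 20 × 1 + 50 × 2 = 120 |
| Recruitment ceiling, no dropout | 20 | 70 | 20 × 1 + 70 × 2 = 160 |

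The last two rows are upper bounds, because the protocol plans for dropout. The first row leaves out baseline scans in women who later drop out.

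**6. Sensitivity to usual PCOS care.** Suppose, against the text, that the baseline scan in women with PCOS were usual care. The added scans among completers would then be 12 + 36 × 1 = 48. If both PCOS scans were usual care, 12 would remain, all in controls. The count reaches zero only if the controls' scans are also clinical care, and nothing in the protocol says so.

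**7. Dose.** None is given, so the scan count cannot be turned into an exposure or a risk.

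**The case against.** Several stronger readings are tempting, and the documents do not support them.

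*A reader might infer that the reproductive-risk paragraph contradicts the DXA paragraph.* It does not. One says that participation adds no radiation; the other says that a DXA scan can affect a fetus. A scan given in ordinary care could also affect a fetus, so both could be true. The fetal hazard is also disclosed and addressed: the protocol requires contraception, and a serum pregnancy test before study procedures and monthly afterwards.

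*A reader might infer that women have consented on a false statement.* The consent form is not in the material reviewed. The protocol presents its risk list as consent wording, which makes a match likely, but the form itself cannot be checked here.

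*A reader might infer that every scan is proven to be added exposure.* For controls the text supports that. For women with PCOS, knowing that a scan is done for research shows its purpose. It does not show what similar patients would otherwise receive.

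*A reader might take 84 or 160 scans as a measure of harm.* Without a dose, the count shows only how often the statement would apply.

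It can also be said that this is a wording error with no effect on design or analysis. That is correct, and it limits the priority of the point. What stands against all these objections is the core: the no-added-radiation statement cannot be reconciled with a research DXA in healthy women.

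**Conclusion.** The point holds as an internal inconsistency in risk disclosure. The no-additional-radiation statement is false for controls (one scan each) and unsupported for women with PCOS (two scans each for completers). On the planned numbers that is 84 protocol scans, of which at least the 12 in controls are added exposure however usual PCOS care is defined.

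This rests on two assumptions: that the schedule is followed with one scan per time point, and that no clinical indication exists for the controls' scans beyond what the protocol describes. The size of the radiation risk is not known from the documents. No endpoint, sample size, allocation or analysis is affected. The text should be corrected, at a priority below the most serious class of finding.

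**What to change.** In Risks of DXA Scan, delete the standard-of-care premise and the no-additional-radiation conclusion. In their place, state that DXA is done for research, with one scan for controls and two for women with PCOS, and give the institution's dose estimate per scan. A cross-reference to Known Reproductive Risks would help the reader. Check the consent form for the same wording and correct it if present.

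The cost is an IRB amendment to the protocol and, if needed, the consent form. No procedure, visit or analysis changes. New wording reaches only later participants. The amendments cited in the protocol show that women were already enrolled by 2013, so the investigators should ask the IRB whether women already scanned need to be told.

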The purpose of this research study is to collect specimen samples and study medical information from women with PCOS and women without PCOS. The goal is to learn more about the changes that take place in the body that result in PCOS.

Revised 3-7-18 UCLA IRB #12-001780 Page 4 of 27

Our Aims are to:

Aim 1: Compare differences in SC abdominal adipose structure-function and regional abdominal adipose content in lean PCOS women vs. age- and BMI-matched controls. Hypothesis: SC abdominal adipose storage is constrained in lean PCOS women.

• Analyze adipocyte size, lipid accumulation, function and secretion of adipokines.

• Analyze same parameters indicated above and signaling pathways in new adipocytes originated from isolated adipose stem cells.

• Use cell culture to examine interactions between adipose stromal-vascular cells and adipocytes in the control of adipose development.

• Correlate key factors with insulin action in vivo; regional and percent body fat; circulating lipids, free fatty acids (FFAs), sex steroids, and adipokines; and ovarian volume, antral follicle number and serum AMH as well as serum E2 response to recombinant human (rh)FSH per antral follicle.

Aim 2. Examine effect of flutamide on SC abdominal adipose structure-function, regional abdominal adipose content and ovarian folliculogenesis in lean PCOS women. Hypothesis: SC abdominal adipose storage is normalized in lean PCOS women receiving flutamide.

• Examine in vitro effects of sex steroids on adipogenesis.

• Determine changes in SC abdominal adipogenesis, circulating lipids, FFAs, sex steroids, and adipokines.

• Determine changes in SC abdominal and visceral adipose content, fat free mass as well as percent body fat.

• Determine changes in ovarian morphology and function as well as ovulatory frequency, as measured by weekly urinary pregnanediol glucuronide (UPDG).

• Determine key factors that predict ovulation by serial urinary UPDG measurements.

RESEARCH DESIGN AND METHODS

Aim 1. Compare differences in SC abdominal adipogenesis of lean PCOS women vs. age- and BMI-matched controls

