Subjects and clinical assessment: We will recruit subjects with the intention of enrolling 90 women - 70 lean (18.5-25 kg/M2) PCOS subjects and 20 age- and BMI-matched controls with the assumption that there will be dropouts such that 36 women with PCOS and 12 controls will complete the study. Subjects will complete a standardized questionnaire emphasizing menstrual dating, abnormal hair growth and acne. The questionnaire also will annotate age, smoking status, medications, surgical history and family histories of excess hair growth in female relatives and of diabetes in parents or siblings for exclusion criteria and for inclusion of some basic traits as covariates. Subjects also will undergo a physical examination; hirsutism will be scored by the modified Ferriman-Gallwey (mFG) method. Transvaginal sonography (TVUS) will be performed to determine the presence or absence of polycystic ovaries by Rotterdam

Revised 3-7-18 UCLA IRB #12-001780 Page 5 of 27

criterion. A screening blood sample will be obtained for determinations of steroid hormones, TSH, and prolactin; biochemical hyperandrogenism will be defined as an elevated serum total or free T > 2 SD above the mean value. Non-Hispanic Caucasian women between the ages of 18 and 35 years will be recruited to avoid confounding differences as a function of race. PCOS patients will be diagnosed by 1990 NIH criteria. Controls will have regular menstrual cycles at 21 to 35 day intervals, a luteal phase progesterone (P4) level > 3 ng/mL, and no evidence of hirsutism, acne, alopecia, polycystic ovaries or endocrine dysfunction. Exclusion criteria are: present/past history of smoking during the past year, cancer, alcohol abuse, drug addiction, severe depression, or post traumatic stress; diabetes; uncontrolled hypertension (\geq 165/100); clinically significant hepatic or renal disease, or other major medical illness; signs or symptoms of infection; recent (within 30 days) use of an experimental device; recent (within 6 months) use of androgens, anabolic steroids or non-steroidal anti-inflammatory drugs; recent (within 3 months) use of hormonal agents (including birth control pills, Plan B, Mirena IUD, or insulin sensitizers); use of the drug warfarin; beta blockers; CYP active medications or herbs.

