Per amendment #42, epigenetic studies (RNA sequencing, DNA Methylation, and Assay for Transposase Accessible Chromatin Sequencing) on existing fat cell samples will be conducted at UCLA.

INCLUSION CRITERIA

Caucasian and Non-Hispanic women between the ages of 18 to 35 years.

Groups will be: 12 lean controls (Aim 1); 36 age- and BMI-matched PCOS women randomized to flutamide vs. placebo for 6 months (Aims 1 and 2).

i) Lean patients with PCOS: 36 subjects with PCOS (defined by 1990 NIH criteria [all Aims]), BMI 18.5-25 kg/m2. This BMI range is defined as normal and has been chosen to examine underlying mechanisms of PCOS-related androgen excess in the genesis of adipogenic and ovarian dysfunction, independent of obesity. Excessive course hair on upper lip, chin, chest, upper back, lower back, upper abdomen, lower abdomen, arm and/or thigh.

ii) Lean control women: 12 healthy subjects, BMI 18.5-25 kg/m2. Controls will have regular menstrual cycles, and no evidence of hirsutism, acne, alopecia, polycystic ovaries, and/or endocrine dysfunction. This BMI range has been chosen to match that of the PCOS group.

Up to 70 lean PCOS patients and 20 lean controls will be recruited, for a total of 90 study participants over a 5-year interval, accounting for a 20% rate of patient drop-out or insufficient adipose procurement. Participants must be fluent in English.

EXCLUSION CRITERIA

Exclusion criteria for study participation are: present or past history of smoking within past 1 year, cancer, alcohol abuse within past 5 years, drug addiction within past 5 years, severe depression within past 5 years, or post traumatic stress disorder within

Revised 3-7-18 UCLA IRB #12-001780 Page 10 of 27

past 5 years; diabetes; uncontrolled hypertension (≥ 165/100); clinically significant hepatic or renal disease, or other major medical illness; recent (within 3 months) use of androgens, anabolic steroids or hormonal agents (including birth control pills or insulin sensitizers), Mirena IUD, or Plan B contraception. These exclusion criteria are chosen to avoid effects from medical conditions, environmental factors or exogenous agents. Women taking the drug warfarin, beta blockers, CYP active medications, or herbs will be excluded.

Since this study involves MRI testing, women with pacemakers, metal implants, or claustrophobia will be excluded.

The screener will assess the participants response to establish if depression or drug use exclude participation in this study.

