We will use one-way factorial analysis of variance (ANOVA) methods to compare continuous outcomes including hormone levels; adipocyte size, lipid content and glycerol release; numbers of ASCs and preadipocytes; mRNA levels. If data are not normally distributed on any scale, we will carry out nonparametric ANOVA.

Our previous comparison of cFOS gene expression in PCOS women vs. controls showed an increase in Δ Ct (6.0 ± 1.4). Based on this, we hypothesize that the mean difference between controls and IR PCOS is 1.7 SD units. Assuming this, a sample size of 8/group (IR vs. non-IR PCOS) provides over 80% power using the usual two-sided p < 0.05.

We also will compare all outcomes before vs. after 6 months of placebo or flutamide treatment controlling for IR status, using either the parametric paired t test or non-parametric Wilcoxon signed rank test. Insulin action and sensitivity will be assessed by calculating a Matsuda Index from blood glucose and insulin levels during the oral glucose tolerance test. Ovarian estradiol sensitivity to FSH will be calculated from the 24-hr area-under-the-curve (AUC) serum estradiol response to FSH infusion.

Based on our in vitro data, we observed a mean 0.17 log scale change in Δ Ct PPAR γ (SD=0.26 log units) after treatment with T + Flutamide vs. T alone. A sample size of 14 (7 non-IR, 7 IR) provides more than 80% power for the IR adjusted mean change.

REFERENCES

3. 2004. Revised 2003 consensus on diagnostic criteria and long-term health risks related to polycystic ovary syndrome. Fertil Steril 81(1):19-25.

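### Aim 1 controls are described as matched on age and BMI, but the planned one-way ANOVA includes neither; adjusting for both gains precision if they predict the outcome

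*Combined protocol and SAP*

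**What the plan says.** - **Comparison.** Aims and Objectives, Aim 1, sets out to "Compare differences in SC abdominal adipose structure-function and regional abdominal adipose content in lean PCOS women vs. age- and BMI-matched controls". The Aim 1 methods and the Inclusion Criteria also describe the groups as matched on age and BMI.
- **How matching is done.** The Inclusion Criteria give shared ranges. BMI is 18.5 to 25 kg/m² in both groups, and for controls the text adds "This BMI range has been chosen to match that of the PCOS group". Age is restricted for everyone: "Caucasian and Non-Hispanic women between the ages of 18 to 35 years". No pairs, sets, calipers or frequency-matching rule are defined.
- **Covariates.** Under Subjects and clinical assessment (Aim 1), "The questionnaire also will annotate age, smoking status, medications" and other history, and this serves "for exclusion criteria and for inclusion of some basic traits as covariates". No list of covariates, model or outcome follows. BMI is not in that questionnaire list, but it is measured under body composition.
- **Analysis.** Statistical Considerations states: "We will use one-way factorial analysis of variance (ANOVA) methods to compare continuous outcomes". A nonparametric ANOVA is the fallback for non-normal data. Neither age, BMI nor the matching is mentioned. The only adjustment named there is for insulin-resistance status, in the before-versus-after comparison.

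**The concern.** A one-way ANOVA has a single factor and no covariates. The design treats age and BMI as important enough to match on, and the methods foresee covariates, but the statistics section carries neither into the model. If age or BMI predicts an outcome, the variance they explain stays in the residual. With 12 controls, precision is limited.

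Three things are at stake:
- **Precision**, for outcomes related to age or BMI.
- **Imbalance.** Any age or BMI difference left after loose matching or drop-out goes into the group comparison uncorrected.
- **Pre-specification.** Because covariates are mentioned but not named, they could be chosen after the data are seen, across many outcomes.

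**Working it through.** **Inputs from the documents.** Planned completers are 36 PCOS and 12 controls. Alpha is 0.05, two-sided. The only between-group effect stated is 1.7 SD, with 8 per group and power over 80%.

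**Assumptions.** R², the share of within-group outcome variance explained by age and BMI, is not given; 0, 0.10, 0.25 and 0.36 are used. The 0.95 SD difference (0.954 unrounded) is illustrative: it is the difference that 36 versus 12 detects with 80% power unadjusted.

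**1. The plan's own figure.** Noncentral t, 8 per group, 1.7 SD: noncentrality = 1.7/√(1/8 + 1/8) = 3.40, df = 14, power 88.5%. The claim of over 80% reproduces.

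**2. The same effect at planned completers.** √(1/36 + 1/12) = 0.333; noncentrality = 1.7/0.333 = 5.10; df = 46; power 99.9%. Adjusted power is 99.8% to 100% over the whole R² range. At this effect adjustment changes nothing that matters.

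**3. Adjustment at 0.95 SD.** The residual SD is multiplied by √(1 − R²) and df falls to 44. Noncentrality = 0.954/[0.333 × √(1 − R²)]. Chance imbalance in two covariates multiplies the variance by about 1 + 2/43 = 1.047.

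| R² | √(1 − R²) | CI narrower by | Noncentrality | Power, balanced | Power, chance imbalance |
|---|---|---|---|---|---|
| unadjusted | – | – | 2.86 | 80.0% | – |
| 0 | 1.000 | none | 2.86 | 79.9% | 78.1% |
| 0.10 | 0.949 | 5% | 3.02 | 83.9% | 82.2% |
| 0.25 | 0.866 | 13% | 3.30 | 89.8% | 88.5% |
| 0.36 | 0.800 | 20% | 3.58 | 93.8% | 92.8% |

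The CI column is for balanced covariates. Adjustment breaks even at R² of about 0.002 (balanced) to 0.05 (chance imbalance).

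**4. Is the unadjusted standard error wrong?** This depends on what matching means.
- *Individual 1:3 matching, 12 exact sets.* The true standard error is √(1 − R²) times the one the test uses. Simulated type I error is about 3.8%, 2.4% and 1.8% at R² = 0.10, 0.25 and 0.36 (runs differ by a few tenths of a point). The test is conservative.
- *Shared ranges only*, both groups drawn independently from the same age and BMI ranges (uniform distributions assumed). Simulated type I error is about 5% at each R². The test keeps its nominal size.

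**5. Imbalance under shared ranges.** The SD of the difference in group mean BMI is 0.333 BMI SDs, so a chance difference of more than 0.33 SD arises about 32% of the time. If PCOS women were systematically 0.5 SD higher in BMI within the range (an assumption), and BMI carried all of R², the unadjusted test would reject a true null from about 7% of the time at R² = 0.10 to about 14% at 0.36.

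**6. Small comparisons.** At 8 per group and 1.7 SD, 88.5% unadjusted becomes 87.7% (balanced) or 81.9% (chance imbalance) at R² = 0, and 93.6% or 89.4% at R² = 0.20. Break-even R² is about 0.03 to 0.18.

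**The case against.** The strongest reply is that a one-way ANOVA is valid here and that adjustment is a preference about efficiency. Most of this stands. The only matching mechanism described is a shared range, and under it the unadjusted test has the right size. A reader might infer that the planned error bars are simply too wide. That would follow only from individual matching, which the documents do not define, together with R² above zero.

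A reader might also infer that the trial loses power it needs. At the plan's own 1.7 SD effect it does not. That defence has a limit, though: 1.7 SD rests on one gene and is stated for controls versus insulin-resistant PCOS, while the Aim 2 text says all PCOS women enrolled so far were non-insulin resistant. Nothing in the documents supports 1.7 SD for hormones, adipocyte size or the other outcomes under the same ANOVA.

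The narrow age and BMI ranges may leave little variance to recover, and no figure links outcomes such as cFOS expression to either variable. That also stands, and is why zero belongs in the range. Nor does the plan disregard covariates altogether: the Aim 1 methods foresee them. The fault is that the statistics section does not say which ones enter which model.

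Finally, adjustment is not free. It costs degrees of freedom, can lose power in very small groups, and removes only linear imbalance.

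**Conclusion.** The point holds as a gap in specification with a modest and conditional cost in efficiency. The design and the covariate sentence point towards adjustment for age and BMI, and the stated analysis omits both.

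At 36 versus 12, the gain for differences near 1 SD is about 4, 10 or 14 percentage points of power at R² = 0.10, 0.25 or 0.36. There is none at R² = 0, where power falls by about 0.1 point with balanced covariates and about 2 points with chance imbalance. There is no material gain at 1.7 SD. These sizes rest on an R² the documents do not supply and on the planned completer numbers.

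The documents do not support calling the unadjusted analysis invalid, or its standard errors biased, as a general statement. Under either reading of matching, adjustment gains precision for outcomes that age or BMI predicts beyond the small break-even R², and it corrects linear imbalance.

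**What to change.** In Statistical Considerations, specify for PCOS versus control a linear model (ANCOVA) with group, age and BMI as pre-specified covariates, with the outcome transformed or a rank-based version where needed. Keep the unadjusted one-way ANOVA as a supportive analysis. Amend the covariate sentence under Subjects and clinical assessment so that both places name the same covariates. State whether controls are matched individually or only by range.

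The cost is a few sentences of wording and 2 of 46 degrees of freedom; age and BMI are already collected. The downside is a small loss of power for outcomes unrelated to age and BMI. It is larger in any comparison of about 8 per group, so the wording should say whether the adjustment applies there too.
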